### 9.4 STATISTICAL ANALYSES

#### 9.4.1 GENERAL APPROACH

Patient characteristics will be summarized per randomized group using percentages if categorical, or means with standard deviations if continuous. These characteristics will be compared using the Wilcoxon rank sum test if continuous, or Fisher's exact test if categorical. Nominal two-tailed p values will be reported. Repeated measures will be analyzed either by linear mixed effects models or by GEE. Standard model diagnostics will be performed.

#### 9.4.2 ANALYSIS OF THE PRIMARY EFFICACY ENDPOINT(S)

The primary endpoint is the average of AF burden at the end of the first week.

We will use Mobile Cardiac Telemetry to determine AF burden before surgery (eligibility visit), for two weeks during ScNS, 3 weeks following surgery and 3 months following surgery.

The average of AF burden at the end of the first week will be calculated per patient as the time spent in AF during the first week divided by the total time a patient is under observation during the first week. Change of the average AF burden from the baseline will be computed for each patient. The change in the average AF burden will be compared between group A (experimental) and group B (control) using the Wilcoxon rank sum test at a two-sided significance level of 0.025.

*The following secondary analyses of the primary endpoint will be performed:*

- 1) We will compare the baseline AF burden and the baseline number of Apple watch-detected AF episodes between groups. The number of Apple watch-detected AF will be standardized by the number of days that a subject is under observation in the respective time period. Further we will compare reduction in AF burden from baseline at weeks 1, 2, 3 and 12 in both Group A and Group B to test the null hypothesis that there is no reduction of AF burden in the two groups and between the two groups. We will also compare the reduction in the number of Apple watch-detected AF episodes from the baseline in the period between week-3 and the end of study in both Group A and Group B to test the null hypothesis that there is no difference in detected AF episodes in the two groups and between the two groups. Linear mixed effect models will be used for the comparisons, with Group, Week and Group by Week interaction as fixed effects, and a random intercept per subject. Week will be coded first as a categorical variable, and appropriate contrasts will be set up for the temporal comparisons. If outcome variables appear to be linear in time, we may model Week as a continuous fixed effect.
- 2) We may also compute the difference-in-difference statistics for the treatment for the 4 time intervals of the treatment, baseline and t weeks 1, 2, 3 and 12.

We may also use generalized estimating equations (GEE) instead of linear mixed effect models if the validity of the latter is suspect. If there is differential drop-out between the randomized groups, we will adjust the group-comparisons using baseline covariates, such as age, sex and heart failure status. Standard approaches for both model checking and selection based QIC will be applied.

---

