# 5 STUDY POPULATION

## 5.1 INCLUSION CRITERIA

In order to be eligible to participate in this study, an individual must meet all of the following criteria:

- 18 to 75 years of age
- Symptomatic paroxysmal AF unresponsive to conventional therapy.
  - Symptomatic paroxysmal AF is defined by paroxysmal AF with patient-reported perception of one or more of the following symptoms: palpitations, dizziness/presyncope, syncope, dyspnea, chest pain, malaise, and fatigue and activity intolerance.
  - There is at least one ECG-documented AF episode.
  - Unresponsive to conventional therapy is defined by not responding to at least 1 antiarrhythmic drug (class I, class III, or atrioventricular nodal blocker).

- The left atrial size <50 mm by transthoracic echocardiography documented by eligibility visit
- Documented atrial fibrillation as defined as atrial fibrillation >30 seconds in duration with an atrial fibrillation burden determined by a minimum of 7 days of continuous ePatch monitoring within 6 months before surgery.

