## 9 STATISTICAL CONSIDERATIONS

### 9.1 STATISTICAL HYPOTHESES

*State the formal and testable null and alternative hypotheses for primary and key secondary endpoints, specifying the type of comparison (e.g., superiority, equivalence or non-inferiority, dose response) and time period for which each endpoint will be analyzed.*

- Primary Efficacy Endpoint(s):

The average AF burden.

- Secondary Efficacy Endpoint(s):

- 1) Time-dependent reduction of AF burden
- 2) Ventricular rate during AF
- 3) Average SKNA
- 4) Quality of life
- 5) Reduction of AF burden after cross over from control to experimental group

**Our primary research hypothesis is that** chronic subcutaneous nerve stimulation can control AF in patients with severe symptomatic AF unresponsive to conventional therapies.

The primary endpoint is the average of AF burden at the end of the first week. Patients who do not experience AF during the first week will have a value of 0 as AF burden. The average of AF burden at the end of the first week will be calculated per patient as the proportion of time spent in AF during the first week divided by the number of days a patient is under observation during the first week.

We will test the null hypothesis of no difference in the average AF burden between the treatment groups versus the alternative hypothesis that the average AF burden is lower in the intervention group than the sham group.

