### 9.2 SAMPLE SIZE DETERMINATION

The AF burden is determined by the amount of time spent in AF detected by Mobile Cardiac Telemetry patch. A recent study analyzed the results of ambulatory single-lead ECG patch sensor monitoring for 11.4 days on average in 7934 men and 5359 women with paroxysmal AF. During the monitoring period, there were a total of 1,041,504 paroxysmal AF episodes. The median daily rate of paroxysmal AF was 1.21 episodes per day (interquartile range [IQR] 0.31-4.99), and the median maximum duration per individual was 7.5 hours (IQR 2.4-18.6 hours). The median burden of AF (% of time in AF relative to entire period of monitoring) was 8.9% (IQR 3.4%-25.2%). Assuming that we implant the lead and randomize patients into experimental group (stimulation) and control group (no-stimulation), we expect to see the same average AF burden among our patients. In our previous study in canine models, subcutaneous nerve stimulation reduced atrial arrhythmia burden per 48 hours from  $211.0 \pm 204.8$  s to  $134.8 \pm 165.2$  s ( $\Delta = -76.3 \pm 44.8$  s) versus a reduction of  $-5 \pm 9.5$  seconds in the sham group. Assuming the same standard deviation of the change of AF burden from baseline in the two randomized groups as 44.8 and accounting for the patient retention rate of 70%, we need 15 per arm (total 30 patients) for 80% power at 2-sided alpha 0.025 to detect an effect size of 1.59 at the end of one week between Group A (experimental) and Group B (control) using the Wilcoxon rank sum test. If the treatment suppresses AF by 75% while the sham does not suppress AF at the end of one week, we have 86% power to detect this difference at 2-sided alpha 0.025 using Fisher's exact test. We have budgeted for 32 patients to ensure that we have sufficient funds to complete the study.

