#### 9.4.3 ANALYSIS OF THE SECONDARY ENDPOINT(S)

The analyses of the secondary endpoints will be performed on the modified ITT data set. Unless otherwise stated, two-tailed nominal p values will be reported.

##### Analysis of mean VR at the end of week 1

In dogs, ScNS reduces ventricular rate during AF. The mean VR was  $149 \pm 36$  bpm after the induction of AF. The VR significantly decreased to  $84 \pm 16$  bpm ( $p=0.011$ ) at the final week of ScNS. The same device that produces AF burden will also generate VR. First, we will summarize the proportion of patients who are AF-free at the end of week 1. Fisher's exact test will be performed to test if the proportions of AF-free patients are the same between the two treatment arms at a two-sided significance level of

0.025. Second, we will summarize the mean VRs using mean and standard deviation by time and by randomization group among the patients who experience AF.

We will classify patients into 3 groups based on the week 1 average VR: patients who do not experience AF as category 1, patients who experience AF with VR  $\leq$  110 bpm as category 2, and patients who experience AF with VR  $>$  110 bpm as category 3. Fisher's exact test will be performed to test if the distribution of the three categories are the same between the two treatment arms and the nominal p-value will be reported.

We will categorize average VR at other time points into three groups as described above, and analyze repeated average VR using ordinal repeated measure analysis with patient as the blocking variable, week and group as well as their interaction as independent variables. Proportional odds assumption will be checked.

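### The primary test ranks raw change in AF burden without adjusting for baseline burden, which varies widely and limits how far each patient can fall; depending on the effect scale, this can cost power

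*Combined protocol and SAP*

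**What the plan says.** - **Primary test (Section 9.4.2).** "The change in the average AF burden will be compared between group A (experimental) and group B (control) using the Wilcoxon rank sum test", at two-sided 0.025. No covariate, stratum or relative scale is named. Section 3 defines burden as the percentage of time in AF, so the natural reading of change is percentage points, though the text never says absolute or relative.
- **Expected baseline (Section 9.2).** From a large patch-monitoring study: "The median burden of AF (% of time in AF relative to entire period of monitoring) was 8.9% (IQR 3.4%-25.2" per cent). The plan expects the same average burden in its own patients.
- **Floor (Section 9.1).** "Patients who do not experience AF during the first week will have a value of 0 as AF burden".
- **Effect assumed (Section 9.2).** The Wilcoxon sample size rests on a constant shift of 1.59 standard deviations, taken from canine data in seconds per 48 hours. A second scenario, for Fisher's exact test, begins "If the treatment suppresses AF by 75% while the sham does not suppress AF at the end of one week".
- **Other analyses.** The mixed models and the difference-in-difference statistics in Section 9.4.2 do not use baseline burden as a covariate. If drop-out differs between arms, "we will adjust the group-comparisons using baseline covariates, such as age, sex and heart failure status". In Section 9.4.3, "Fisher's exact test will be performed to test if the proportions of AF-free patients are the same between the two treatment arms", at 0.025.
- **Source of baseline (Section 5.1).** AF burden is "determined by a minimum of 7 days of continuous ePatch monitoring within 6 months before surgery".

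**The concern.** A patient's possible fall in burden is capped by that patient's own baseline. Someone at the lower quartile whose AF disappears completely falls by 3.4 points. Someone at the upper quartile who improves by only 20% falls by 0.20 x 25.2 = 5.0 points, and so ranks as the better responder. If the treatment works proportionally, the spread in baseline becomes spread in change within the treated arm, and the rank test treats it as noise.

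About 10 patients per arm are expected to be evaluable, each after a surgical lead placement, so lost power is hard to recover. The plan compares baseline burden between arms but makes no use of the result in the primary test. Randomisation is described without stratification by burden.

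**Working it through.** **1. The plan's own figure.** Effect size = (76.3 - 5)/44.8 = 1.59. By simulation with a normal shift of 1.59 SD at two-sided 0.025, the Wilcoxon test has 78% power (exact p) or 74% (normal approximation) at 9 per arm, and 83% or 80% at 10 per arm. Ten evaluable patients divided by 0.70 retention is 14.3, rounded up to 15 per arm. The stated sample size is reproduced.

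**2. Room to fall.** The quartiles differ by 25.2/3.4 = 7.4-fold. Under a 75% reduction, a patient at the lower quartile drops 0.75 x 3.4 = 2.6 points and one at the upper quartile 0.75 x 25.2 = 18.9 points.

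**3. Chance imbalance at baseline.** A log-normal fit to the quartiles gives log SD = ln(25.2/3.4)/1.349 = 1.48. The probability that the arms' geometric-mean baselines differ at least 2-fold is 2 x [1 - Phi(ln 2/(1.48 x sqrt(2/n)))]: 0.30 at n = 10 per arm and 0.20 at n = 15.

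**4. Power, unadjusted against adjusted.** Simulation at 10 per arm, two-sided 0.025, 3,000 runs per cell, permutation p-values, log-normal baseline capped at 100%. The adjusted test ranks the change, regresses it on the rank of baseline, and compares residuals between arms. Assumption: the within-patient log SD of week 1 against baseline is not in the documents, so 0.3 to 1.0 is shown. There are no zero weeks in this table.

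| Proportional reduction | Noise SD 0.3 | Noise SD 0.5 | Noise SD 1.0 |
|---|---|---|---|
| 75% | 87% vs 99% | 72% vs 95% | 38% vs 51% |
| 50% | 70% vs 91% | 41% vs 52% | 12% vs 14% |
| 36% (canine, 76.3/211.0) | 47% vs 60% | 21% vs 24% | 6% vs 7% |

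A wider grid added a logit-normal baseline and up to 15% zero weeks:

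| Scenario | Unadjusted | Adjusted | Gain (points) |
|---|---|---|---|
| 75% reduction | 28-92% | 41-99% | 7 to 29 |
| 75% reduction, extra noise in the baseline recording (SD 0.5-1.0) | 22-61% | 47-91% | 25 to 34 |
| 50% reduction | 11-82% | 13-96% | 1 to 21 |
| 36% reduction | 7-64% | 7-80% | 0 to 17 |
| 75% of treated patients AF-free, no sham patients | 36-63% | 47-66% | 3 to 12 |

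The noisier-baseline row is relevant because the baseline recording may be up to six months old. Of 120 non-null proportional cells, including some with 25% zero weeks, the adjusted test was lower in 2, each by 0.2 points or less.

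**5. The plan's additive model (1.59 SD).** Without a floor: 81-83% unadjusted, 79-82% adjusted. With burden floored at zero and an assumed SD of change of 2-8 points: 55-74% against 63-75%. At an SD of 1 point: 78% against 77%.

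**6. Validity.** With no effect, both tests reject in 2-3% of runs.

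**7. The form of the adjustment matters.** Ranking the follow-up value, not the change, against baseline rank drops to 28-58% under the unfloored additive model. Ranking the change gives 80-81% there.

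**The case against.** The strongest reply is that nothing here is an error. A rank sum test on change controls type I error, randomisation already allows for chance imbalance, and subtraction uses baseline in part. All of that stands, and the point is one of efficiency only.

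Next, under the additive model that sizes the Wilcoxon test, adjustment loses about 2 points. The 75% figure belongs to the Fisher scenario. Read as the share of patients who become AF-free, it brings a gain of 3-12 points, not 7-29. The one observed effect cited, in dogs, gives 0-17. This also stands and is why the conclusion is conditional. However, the unfloored additive case ignores the plan's own scoring of AF-free weeks as 0. With the floor in place, adjustment ranges from a loss of about 1 point to a gain of 9.

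The choice of method is also open to debate. Log-scale covariance analysis does better when no week is AF-free. In one setting with 15% zero weeks coded as 0.01 it fell to 23%, against 79% for the rank method. That favours a method that tolerates zeros.

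Finally, the safety-set sensitivity analysis in Section 9.3 assigns zero reduction to patients without a baseline, who have no baseline rank. The adjusted test cannot be run on them. The unadjusted test can serve there, and missing baselines should be rare because Section 5.1 requires a recording.

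**Conclusion.** The concern holds as a conditional loss of efficiency, not a flaw in validity. The primary test makes no use of baseline burden beyond subtraction, and no other planned analysis uses it as a covariate. The potential gain from adjustment is lopsided: up to 29 points of power for a large proportional effect (up to 34 with a noisier baseline recording), against a loss of about 2 points if the effect is purely additive with no floor. There is little or no gain if the effect is small or within-patient noise is high.

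These sizes rest on about 10 evaluable patients per arm, on baseline distributions fitted to the quartiles in Section 9.2, and on assumed values for within-patient noise and the frequency of AF-free weeks. They also rest on reading change as absolute. The change is worth making, but the trial would remain interpretable without it.

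**What to change.** - Keep change in AF burden as the primary variable and two-sided 0.025. Replace the unadjusted test with this one: rank the change (average ranks for ties), regress it on the rank of baseline burden, and compare the residuals between arms with a permutation p-value.
- Keep the unadjusted Wilcoxon test as a prespecified sensitivity analysis, and use it for the safety-set analysis in Section 9.3.
- State that change is absolute, and say whether the expected effect is additive or proportional.
- Report relative change by arm with a confidence interval. It is defined for every patient in the modified intention-to-treat set, since patients without AF at baseline are excluded (Section 5.2). Use medians: Section 5.1 sets no minimum burden, and percentages are unstable at very small baselines.

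**Cost.** No new data are needed, because baseline burden is already required for the modified intention-to-treat set. The test becomes slightly more complex, with about 2-3 points of power lost in the worst additive case. The change needs an amendment with IRB approval while the trial is under way; Section 10.4 shows that patients have already been stimulated. The investigators know the allocation (Section 4.1), so the amendment should be written by people without access to outcome data by arm.

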We will compare the number of Apple watch-detected AF episodes between week-3 and the end of study between Group A and Group B to test the null hypothesis that there are no differences in detected AF episodes between the two groups. For each patient, we will record the number of days that the patient is under observation, and the number of days that AF episodes are detected. Assuming that each patient's data follows a binomial distribution and the probability of AF daily detection is the same within group. Since patients' data are independent from each other and the sum of independent binomials are still a binomial, we can compare the two groups as two binomials with potentially different rates of AF detections. Fisher's exact test will be performed for this comparison at a two-sided significance level of 0.05.

The overall scores of Quality of life (AFEQT-AF, EQ-5Q-5L) questionnaires will be compared at the following time points, baseline, 3 week and 3 month visits by the same linear mixed effect models as described for aSKNA. The same missing data treatment as stated above will be employed in the linear mixed model analyses of these two outcomes. Item and total scores may be transformed if deemed necessary to fulfil model assumptions.

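### The primary test and an unlisted AF-free test each get two-sided 0.025 with no stated overall alpha or recycling; Holm would reject at least as often at the same familywise error

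*Combined protocol and SAP*

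**What the plan says.** Section 9.4.2 declares one primary endpoint: "The primary endpoint is the average of AF burden at the end of the first week". Its change from baseline is compared between arms "using the Wilcoxon rank sum test at a two-sided significance level of 0.025".

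Section 9.4.3 reports nominal p values unless it says otherwise. Under its heading on mean ventricular rate at week 1 it does say otherwise. A Fisher test will "test if the proportions of AF-free patients are the same between the two treatment arms at a two-sided significance level of" 0.025. AF-free status does not appear among the endpoints in sections 1.1, 3 or 9.1, nor among the primary and secondary hypotheses in 9.1.

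Section 9.2 gives each test its own power at that level. For the Wilcoxon test, "we need 15 per arm (total 30 patients) for 80% power at 2-sided alpha 0.025 to detect an effect size of 1.59". For a Fisher test of AF suppression (75% against none), it states 86% at two-sided 0.025.

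One further comparison, of Apple Watch detections after week 3, has a stated level: "Fisher's exact test will be performed for this comparison at a two-sided significance level of 0.05".

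No section states an overall alpha, gives a reason for 0.025, or says what a positive AF-free test would allow the trial to claim.

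**The concern.** A single primary endpoint would ordinarily carry the whole significance level. Here it carries 0.025, and a second test on the same week's AF data carries another 0.025. The natural reading is that 0.05 was divided equally between two tests, with nothing passed on when one succeeds.

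Two things are at stake.

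- **Interpretation.** Suppose the Wilcoxon test gives p = 0.20 and the AF-free test p = 0.02. The plan does not say whether the trial has succeeded, and the significant result belongs to an outcome that no list contains.
- **Efficiency.** Suppose instead that the AF-free test gives p = 0.02 and the Wilcoxon p lies between 0.025 and 0.05. The present rule rejects only the unlisted outcome. A step-down rule with the same familywise error would reject both.

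**Working it through.** **Inputs from section 9.2.** Canine reductions of 76.3 s (stimulated) and 5 s (sham); SD of change 44.8 s; 70% retention; 80% power; two-sided 0.025; Wilcoxon rank sum test; AF suppression of 75% versus 0%.

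**1. Reproduce the sample size.** Effect size = (76.3 − 5)/44.8 = 1.59. The exact two-sided Wilcoxon test was simulated with 100,000 normal-shift trials per case. At 0.025, power is 78.1% with 9 evaluable per arm and 82.6% with 10, so 10 are needed. Then 10/0.70 = 14.3, which rounds up to 15 per arm. The stated 15 per arm reproduces, and the 80% target is met at the level actually used.

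**2. Same patients, level 0.05.** With 10 evaluable per arm, power is 89.1%. The most that any recycling rule could add to primary power at this design point is 89.12% − 82.56% = 6.56 points.

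**3. Sum of the two levels.** 0.025 + 0.025 = 0.05, which fits a Bonferroni split.

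**4. Holm in place of the split.** Compare the smaller p with 0.025; if it is rejected, compare the other with 0.05. The primary is then rejected if its p is at most 0.025, or if its p lies between 0.025 and 0.05 and the AF-free test is significant at 0.025. Treating the tests as independent:

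primary power = 0.8256 + 0.0656 × F,

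where F is the Fisher power at 0.025 with 10 per arm, by full binomial enumeration.

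| AF-free rates (ScNS vs sham) | F | Primary power, present split | Primary power, Holm |
|---|---|---|---|
| 75% vs 0% | 0.922 | 82.6% | 0.8256 + 0.0656 × 0.922 = 88.6% |
| 50% vs 10% | 0.209 | 82.6% | 0.8256 + 0.0656 × 0.209 = 83.9% |
| 30% vs 10% | 0.021 | 82.6% | 0.8256 + 0.0656 × 0.021 = 82.7% |

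The first row is the scenario in 9.2, read as the share of patients who are AF-free. The other two rows are assumptions that show the range.

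**5. Nothing is lost.** Any p at or below 0.025 is rejected under both rules, so Holm rejects everything the present rule rejects. Holm holds the familywise error at 0.05 whatever the dependence between the tests.

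**6. Side check.** The 86% Fisher figure does not reproduce for 75% versus 0% at 0.025: 83.4% with 9 per arm, 92.2% with 10, 96.6% with 11. With sham at 5% it is 83.8% with 10 and 88.3% with 11. The inputs behind 86% should be stated when 9.2 is revised.

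**The case against.** The strongest reply is that 0.025 is a conservative choice that the trial can afford. The sample size was derived at that level, the 80% target is met, and type I error on the primary is not inflated. All of that stands.

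A reader might go further and infer that half the alpha is wasted. The documents do not support this. Section 9.2 gives the Fisher comparison its own power figure, so it looks like an intended second route to success, and that is what the second 0.025 buys. No section states a 0.05 family either; the split is an inference. Another conceivable source of 0.025 is the directional hypothesis in 9.1, "the alternative hypothesis that the average AF burden is lower in the intervention group than the sham group". That fits less well, because both levels are stated as two-sided.

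A reader might also add the Apple Watch level and report a total of 0.10. That is only a sum of stated levels. The Apple Watch comparison sits in a section whose default is nominal p values, and nothing places it in one confirmatory family with the primary.

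Finally, the full gain to about 89% is not guaranteed under Holm. It depends on the AF-free test succeeding, and it nearly vanishes if few patients become AF-free. This also stands.

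**Conclusion.** The point holds as one of specification and efficiency. Two tests each carry two-sided 0.025, one of them has no endpoint status, and there is no overall alpha, decision rule or recycling. The trial is not underpowered against its own plan.

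The efficiency gain from Holm runs from almost nothing to about 6 points of primary power, depending on how many patients become AF-free.

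The size rests on these assumptions:

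- the canine effect size of 1.59;
- 10 evaluable patients per arm;
- a normal shift, although 9.2 describes human AF burden as skewed;
- independence of the two tests, although both use the same week-1 recordings. Dependence would change the gain, but not beyond the range of 0 to 6.56 points at this design point.

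That Holm never rejects less than the present split, at the same familywise error, rests on none of these assumptions.

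**What to change.** 1. In 9.1, list the AF-free proportion at week 1 as an endpoint, with its hypothesis and status, and say what a positive result would support if the primary test fails.
2. State an overall two-sided alpha of 0.05 across the primary Wilcoxon test and the AF-free Fisher test.
3. In 9.4.2 and 9.4.3, replace the two fixed levels with Holm: smaller p against 0.025 and, if it is rejected, the other against 0.05.
4. In 9.4.3, label the Apple Watch comparison as nominal.
5. In 9.2, restate power under this rule and give the inputs for the Fisher figure.

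**Cost.** No added patients or assessments. It is a change of wording, but it needs IRB approval as an amendment. The amendment history (10.4, version 11) shows that patients have already been treated, and 4.1 says the investigators are not blinded. The change should therefore be made and dated before any comparison of outcomes by arm.

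**Alternative, not recommended.** A fixed sequence with the primary always at 0.05 gives about 89% primary power whatever the AF-free rates. It gives up the AF-free test as an independent route to success, and it loosens the primary level mid-trial with unblinded investigators. That is a trade-off; Holm gives up no rejection that the present rule allows.
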